2.4.4 Inclusion/Exclusion Criteria

Table 1 lists the inclusion and exclusion criteria common to both patient study arms.

Inclusion Criteria	Exclusion Criteria
Age \geq 60	Implanted pacemaker
Surgery requiring cardiopulmonary bypass for Coronary artery bypass grafting (CABG), aortic repair/replacement, septal myectomy, and/or heart valve repair/replacement	Automatic internal cardiac defibrillator
English Speaking	Other implant for which MRI is contraindicated
	Concomitant cerebrovascular procedure or requirement of deep hypothermic circulatory arrest
	Inability to lay flat or still for MRI
	Legal blindness or severe deafness
	Seizure history
	Known focal brain lesion larger than 3 cm

Table 1: Common Inclusion and Exclusion Criteria for Study Enrollment

Delirium Case Arm: Delirious as diagnosed by the Confusion Assessment Method (CAM)/Confusion Assessment Method for the Intensive Care Unit (CAM-ICU) at some point during postoperative day 1-5. The presence of hypoactive delirium will be confirmed after consent has been obtained and prior to measurements.

Postoperative Control Arm: Not delirious as diagnosed by the CAM on postoperative day 1-5.

2.4.5 Study Involvement

Preoperative Testing: Approximately 2 hours. This will occur within one month before surgery and will take approximately 2 hours total. A baseline CAM assessment will be completed at this time. Research personnel will also assess for pain using the Behavioral Pain Scale for Non-Intubated Patients (BPS-NI). Patients will then be asked to sit upright and still for 30 minutes while watching television or moving toes or fingers to maintain wakefulness. EEG and fcDOT data will be acquired. An additional 15 minutes of data will be acquired while patients keep their eyes closed. To maintain wakefulness, patients will be asked to keep moving toes or fingers. Patients will also listen to an auditory recording for 3 minutes while EEG and fcDOT data is acquired for source localization. Patients will then be asked to remain awake and still in an MRI scanner for 1 hour to allow fMRI data to be acquired. The MRI may not be performed on the same day as preoperative EEG and DOT due to the availability of the scanner. Pulse oximetry may be used during data acquisition, with supplemental oxygen, if needed.

Postoperative Sessions 1-3: Approximately 1 hour each. These sessions will occur between postoperative days 1-8. A CAM assessment will be completed to determine delirium outcome prior to other procedures. If patients are intubated at the time of assessments, the Confusion Assessment Method for the Intensive Care Unit (CAM-ICU)[62] will be used. If the patient is sedated (RASS level -4 or -5), delirium will not be assessed. Patients may also be assessed using the CAM-ICU if the patient's current condition cannot tolerate the long-form of the CAM. Research personnel will also assess for pain using the Behavioral Pain Scale (BPS)/Behavioral Pain Scale for Non-Intubated Patients (BPS-NI), depending on the status of the patient, and the Visual Analog Scale (VAS) pain scores. Patients will then be asked to sit upright and still for three 10 minute periods while watching television or moving toes or fingers to maintain wakefulness. EEG and fcDOT data will be acquired. An additional 15 minutes of data will be acquired while patients keep their eyes closed. To maintain wakefulness, patients will be asked to keep moving their toes or fingers. Patients will also listen to an auditory recording for 3 minutes while EEG and fcDOT data is acquired. These data will maximize interpretability by allowing localization of auditory cortex. Pulse oximetry may be used during data acquisition, with supplemental oxygen, if needed.

Session 4-5: Approximately 2 hours. This will occur during the period between disconnection of chest tubes and within 1 month after hospital discharge. A CAM assessment will be completed to determine delirium outcome prior to other procedures. Patients may also be assessed using the CAM-ICU if the patient's current condition cannot tolerate the long-form of the CAM. Research personnel will assess for pain using the Behavioral Pain Scale (BPS)/Behavioral Pain Scale Non-intubated (BPS-NI), depending on the status of the patient, and the Visual Analog Scale (VAS) pain scores. Patients will be asked to sit upright and still for 30 minutes while watching television or moving toes or fingers to maintain wakefulness. EEG and fcDOT data will be acquired. An additional 15 minutes of data will be acquired while patients keep their eyes closed. To maintain wakefulness, patients will be asked to keep moving toes or fingers. Patients will also listen to an auditory recording for 3 minutes while EEG and fcDOT data is acquired for source localization.

Patients will then be asked to remain awake and still in an MRI scanner for 1 hour to allow fMRI data to be acquired. Due to the availability of the scanner, patients may undergo the MRI scan on a different day as the session 4 fcDOT and EEG recording session. A CAM assessment will be completed on the day of the scan to assess delirium. Pulse oximetry may be used during data acquisition, with the administration of supplemental oxygen, if needed.

Subjects may be contacted after session 4 to ask about their health status.

Chart Review: We will continually monitor the participant's electronic medical record (EMR) during their enrollment to ensure you remain eligible for study procedures and to help coordinate timing of study procedures. In addition, we will collect information pertaining to the participant's surgery, recovery progress, and indicators of delirium. We will continue to access the participant's EMR after discharge from the hospital.

2.4.6 Intervention: None

2.4.7 Observations and Measurements

2.4.7.1 Electroencephalography Acquisition and Processing (Aims 1).

Skin of patients will be prepped in the following manner. An alcohol swab will be used to degrease the sites. Gentle debridement of dead skin cells will be performed using a sponge and ELPREP (Biopac) prior to placement of electrodes. If detected, high impedance (> 50 kOhm) electrodes will be replaced to maximize signal quality and minimize electrical artifact.

EEG will be recorded using Biopac MP150, wireless Bionomadix transmitters, and AcqKnowledge 4.2 (Biopac Systems, Inc. Goleta, CA). Data will be acquired at 200 Hz. These will be visualized assessed online for EEG motifs associated with light non-rapid eye movement sleep (K-complexes and sleep spindles). During acquisition, patients will be awakened if these are noted. As these motifs have not been described in awake delirious patients, epochs with these periods will be excluded during analysis.

Using a bandpass filter (0.5-35 Hz), slow drift, EMG, and electrical artifact will be reduced in the EEG recordings. Power spectral analysis will be performed on the first 1 minute of artifact-free data. Total power (TP) will be computed between 0.5 and 30 Hz. Relative Delta Power will be calculated as power between 0.5-4 Hz / TP. Relative Theta Power will be calculated as power between 4-8 Hz / TP. Relative Alpha Power will be calculated as the power between 8-12 Hz / TP. These measures will be calculated for each patient during eyes open and eyes closed epochs, and during both delirium and after resolution.

2.4.7.2 fcDOT processing, and FC analysis (Aims 2).

High-density fcDOT will be performed using a clinical CW imaging system (near-infrared wavelengths of 750 nm and 850 nm, 48 sources and 34 detectors) paired with optical fibers embedded in a wearable imaging cap. This

cap (Figure 4C-D) will provide coverage over DMN components that are anterior (dorsolateral middle frontal gyrus, MFG) and posterior (inferior parietal lobule, IPL). Patients will be instructed to keep their eyes open and to stay awake for three 10-minute runs. Pre-processing will continue as previously described[58]. Briefly, source-detector measurements will undergo log-mean transformation prior to filtering, reconstruction, spectroscopy, and transformation to MNI atlas space. Superficial signal regression and a motion censoring metric similar to DVARS will be used to reduce physiologic and motion artifacts. Bandpass filtering (0.009-0.8 Hz), Pearson correlations will be Fisher z-transformed prior to averaging to maximize normality. The median DMN FC taken across all DMN region pairs will serve as our summary metric for DMN integrity at an individual level.

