Measurements	
Primary:
 
(1) EEG before surgery, during delirium, and after recovery: Delta (0.5-4 Hz), theta (4-8 Hz), and alpha (8-13 Hz) EEG power from 1 minute of continuous artifact-free data acquired during 30 minutes of eyes open wakefulness and 15 minutes of eyes closed wakefulness within one month before surgery and after surgery between POD 1-8.
 
(2) FC Diffuse Optical Tomography (fcDOT) before surgery, during delirium, and after recovery: FC between anterior and posterior DMN regions assessed from a total of 30 minutes of fcDOT data with eyes open wakefulness, a total of 15 minutes of eyes closed wakefulness, and 3 minutes while listening to an audio recording within one month before surgery and after surgery between POD 1-8.
 
(3) Non-contrast fcMRI of patients before and after surgery in both individuals who do and do not develop delirium: FC between anterior and posterior DMN regions assessed from 20 minutes of resting-state fcMRI acquired with eyes open wakefulness within one month before surgery and after surgery during the period between disconnection of chest tubes and within 1 month after hospital discharge.
 
Secondary:
 
(1) fcDOT and EEG from patient controls
 
(2) Patient Demographics, including age and years of education, surgical and anesthetic exposure

Outcomes	
(1) Delirium incidence as assessed by the CAM/CAM-ICU.
 
(2) Delirium severity subscores as assessed by the CAM-S.
 
(3) Delirium duration as the number of days with CAM+ listed in patient records.
 
(4) Pain level using the BPS/BPS-NI and VAS Pain scores.

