2.1.5 The Default Mode Network

The Default Mode Network (DMN)[42] is an archetypal RSN[43] widely distributed across the cerebral cortex (**Figure 1**). The DMN contains regions that are most active during quiet resting[42] and are negatively correlated with those of other RSNs implicated in attention[44] and salience detection[45]. It plays a putative role in self-referential cognition and episodic memory[46]. Reduction of FC within the DMN occurs during slow-wave sleep[47, 48], coma[49], and anesthetic-induced unconsciousness[41, 50], and correlates with severity of Alzheimer's dementia[51, 52]. Moreover, alterations in DMN FC precede clinical dementia symptoms[53-55]. These observations are consistent with our hypothesis that latent DMN FC abnormalities in ostensibly normal patients reflect susceptibility to perioperative delirium. Our fcMRI study of healthy volunteers rendered unresponsive with sevoflurane demonstrated weakening of FC within the DMN (**Figure 2**)[41], suggesting that DMN FC is likely weakened during general anesthesia. Whether inflammation and surgical factors implicated in delirium pathogenesis converge on a vulnerable DMN remains unknown. Reduced DMN FC, as a marker of delirium, is supported by the weakening of DMN MRI FC between anterior and posterior regions during delirium compared to control patients (**Figure 3**)[56]. While suggestive, the role DMN FC as a MRI marker of delirium pathogenesis has not been established.

[figure not shown]

Figure 1. Superficial and deep regions of the Default Mode Network (DMN). Transverse and sagittal atlas sections with superimposed resting-state networks (RSNs) are shown. The DMN (red) contains deep regions (mPFC and PCC) and superficial cortical regions (MFG and IPL). Temporal regions are not shown. Other RSNs are shown in different colors. Adapted from [name] et al., 2015[41].

[figure not shown]

Figure 2. Reduction of DMN FC during sevoflurane sedation. **A.** PCC region. **B.** Transverse and sagittal sections showing PPC FC to the medial prefrontal cortex (mPFC) and superficial regions of the inferior parietal lobule (IPL) or middle frontal gyrus (MFG). **C.** During unresponsiveness induced by 1.2% sevoflurane, FC between the PCC and both anterior DMN components (mPFC and MFG) and posterior DMN (IPL) is weakened. Average **D.** FC among DMN regions is significantly reduced ($p < 0.05$, unpaired t-test). A: Anterior. P: Posterior. Adapted from [name] et al., 2015[41].

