2.1.7 Bedside Functional Neuroimaging

Recent work by members of our team ([name], [name]) have allowed the generation of high density diffuse optical tomography systems for assaying task-evoked and resting-state functional connectivity. The imaging system relies on fiberoptic cables implanted in a wearable cap. The fibers are arranged in a grid such that sources and detectors are interspersed along the scalp to allow measurements of near-infrared light (750 nm and 850 nm) in a manner similar to cerebral oximetry. Preprocessing of multiple overlapping measurements of light intensity include source modeling, spectroscopy, and atlas reconstruction to generate oxy- and deoxyhemoglobin maps as a surrogate of neural activity. fcDOT has been recently validated against fcMRI[58, 59], with superficial regions of the DMN accessible by fcDOT[58] (**Figure 4A-B**). A portable clinical system has also been developed[60]. Using this system, fcDOT is currently in use for bedside imaging of RSNs during natural sleep with simultaneous EEG lasting several hours ([name], [name], [name], **Figure 4C-E**). Sleep staging and censoring of motion artifact is performed prior to FC analysis. Maps plotting FC to a left frontal region demonstrate bilateral connectivity during rapid eye movement sleep (REM) that is reduced during slow wave sleep (SWS). As EEG during delirium demonstrates slower frequencies in a similar manner as SWS and other sleep stages, these data lend feasibility toward imaging fluctuations in FC that mirror established electrophysiologic correlates and symptomatology. As shown in **Figure 4G**, the cart and fibers of the portable fcDOT system are not expected to impact clinical care, even in the intensive care unit.

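### The plan drops sleep epochs from the EEG for Aim 1 but states no matching exclusion for the fcDOT recorded in the same sessions, which can bias Aim 2 towards its hypothesis

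*Combined protocol and SAP*

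**What the plan says.** All references are to the combined protocol and SAP.

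- **EEG, 2.4.7.1 (headed for Aim 1).** The recording is watched online for K-complexes and sleep spindles. "During acquisition, patients will be awakened if these are noted". For the analysis: "As these motifs have not been described in awake delirious patients, epochs with these periods will be excluded during analysis". Spectral power then comes from the first artifact-free minute.
- **fcDOT, 2.4.7.2 (headed for Aim 2).** Wakefulness is controlled by instruction: "Patients will be instructed to keep their eyes open and to stay awake for three 10-minute runs". The cleaning steps are "Superficial signal regression and a motion censoring metric similar to DVARS will be used to reduce physiologic and motion artifacts", together with filtering and reconstruction. No step refers to sleep or arousal.
- **Recording, 2.4.5.** EEG and fcDOT belong to the same sessions. For the auditory run this is explicit: "Patients will also listen to an auditory recording for 3 minutes while EEG and fcDOT data is acquired". For the resting runs it is implied. Patients watch television or move toes or fingers to stay awake.
- **Synopsis, Measurements.** The primary fcDOT measurement also lists "a total of 15 minutes of eyes closed wakefulness".
- **Background.** Section 2.1.5 states: "Reduction of FC within the DMN occurs during slow-wave sleep[47, 48], coma[49], and anesthetic-induced unconsciousness[41, 50". Section 2.1.7 reports reduced fcDOT connectivity in slow-wave sleep in the team's natural-sleep recordings, where "Sleep staging and censoring of motion artifact is performed prior to FC analysis".
- **Statistical sections.** Section 2.5.1 (Aim 1) concedes that patients may not stay awake, above all with eyes closed, and adds a check of the EEG for sleep. Section 2.5.2 (Aim 2) specifies a paired signed-rank test with no arousal term and does not mention sleep. Sections 2.5.3 and 2.5.4 raise sleep as a confounder of fcMRI and offer changes in recording, not exclusion.

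**The concern.** Aim 2 asks whether DMN connectivity is weaker during delirium than after it resolves in the same patient. Sleep lowers the same quantity in the same direction. If the delirium session contains more sleep than the recovery session, the paired difference contains a sleep component that the signed-rank test cannot separate from delirium.

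The plan treats this as serious enough in the EEG to need both waking and exclusion. For fcDOT only the waking carries over, because it acts on the patient and not on the data. Whatever was recorded between the onset of sleep and the moment of waking stays in the fcDOT correlation unless something removes it.

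At stake is how a positive Aim 2 result is read. Section 2.5.2 would take lower connectivity during delirium as support for using it to screen for delirium. That needs the signal to be specific to delirium rather than to sleep.

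**Working it through.** **1. The text.** The plan has three kinds of protection against sleep:

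| Protection | EEG (Aim 1) | fcDOT (Aim 2) |
|---|---|---|
| Instruction, television, toe or finger movement | yes | yes |
| Online waking when motifs appear | yes | yes, in simultaneous recordings |
| Exclusion of sleep epochs from the analysis | yes (2.4.7.1) | not stated |

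**2. Exposure.** EEG power uses 1 minute. The fcDOT estimate uses 3 × 10 = 30 minutes with eyes open. If the eyes-closed data in the synopsis also enter, it uses 30 + 15 = 45 minutes. Section 2.4.7.2 describes only the eyes-open runs, so it is unclear which applies. Either way, the longer series lacks a stated exclusion.

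**3. Direction.** Sections 2.1.5 and 2.1.7 put connectivity lower in slow-wave sleep. Aim 2 predicts lower connectivity in delirium. The bias has the sign of the hypothesis, provided that sleep is more common in delirium sessions.

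**4. Size (illustration).** The plan states no figure to reproduce here; its power statement in 2.6 concerns the between-group comparison.

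Inputs:
- n = 33 pairs, from the planned delirium arm in the synopsis.
- Two-sided alpha 0.05: assumed, as the plan states none.
- f, the excess share of sleep in delirium over recovery sessions: assumed 0.1 to 0.4.
- D, the drop in connectivity from wake to full sleep, in SDs of the paired difference: assumed 0.5 to 2.
- Session connectivity falls in proportion to the share of sleep: assumed.

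Shift = f × D. The signed-rank test was simulated 4,000 times per cell on normal differences with no true delirium effect. Share significant:

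| f | D = 0.5 | D = 1 | D = 2 |
|---|---|---|---|
| 0.1 | 6% | 8% | 19% |
| 0.2 | 8% | 21% | 58% |
| 0.3 | 13% | 38% | 91% |
| 0.4 | 20% | 59% | 99% |

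With f = 0 the rate is about 5%. Only the product f × D matters: the three cells with a shift of 0.2 SD (19%, 21%, 20%) differ by simulation error alone.

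**5. Hand check.** Take the signed-rank test's relative efficiency of 0.955 under normality, and let λ = shift × √(33 × 0.955) = shift × 5.61. The rejection rate is about Φ(λ − 1.96) + Φ(−λ − 1.96).
- Shift 0.1: λ = 0.56, rate 0.081 + 0.006 = 0.087.
- Shift 0.2: λ = 1.12, rate 0.201 + 0.001 = 0.202.
- Shift 0.3: λ = 1.68, rate 0.391 + 0.000 = 0.391.

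These agree with the simulated 8%, 20% and 38%.

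**The case against.** **The plan is silent; it does not say that sleep is kept.** A reader might infer a decision to leave sleep in the fcDOT data. The documents do not support that. The exclusion sentence names no modality, and 2.4.7.2 is a short summary that refers to an outside source for the rest. This stands. Still, the section and heading tie the rule to EEG and Aim 1, and an analyst following 2.4.7.2 as written would not apply it.

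**Safeguards already limit sleep.** Online waking at light-sleep motifs makes slow-wave sleep less likely, and slow-wave sleep is the state for which the documents report lower connectivity. Section 2.5.4 also allows 5-minute epochs when patients cannot stay awake for 10-minute scans. The sentence before it concerns fcMRI, but the 10-minute runs that the protocol specifies are the EEG and fcDOT runs, so it may cover fcDOT. Both reduce exposure. Neither removes sleep already recorded.

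**Unequal sleep is not shown.** No passage says that patients sleep more in delirium sessions, and 2.1.2 describes arousal as maintained in hypoactive delirium. This stands: the imbalance is plausible, not documented.

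**Section 2.1.7 is not a precedent for deletion.** Staging there serves a comparison of sleep stages. It shows that sleep can be identified alongside fcDOT, no more.

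**Aim 3.** A reader might extend the bias to the case-control comparison. Objective 2 in the synopsis compares connectivity after recovery with controls. On that reading, sleep in delirium sessions does not enter, and the bias there is weak.

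**Conclusion.** The point holds as a gap in the fcDOT specification for Aim 2. That the exclusion is stated for EEG and for nothing else follows from the text. That sleep recorded before waking would then remain in the fcDOT estimate follows from applying 2.4.7.2 as written. That this biases Aim 2 towards its hypothesis depends on one condition the documents do not quantify: more such sleep during delirium than after recovery.

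The size is unknown. Across the assumed grid the false-positive rate runs from 6%, close to nominal, to 99%, so no single cell should be read as the expected error rate. The figures show that a modest shift matters with 33 pairs, not that one will occur.

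A reader might also infer that drowsiness in general will be reported as weak connectivity. The documents establish the effect for slow-wave sleep only, and the EEG rule marks K-complexes and spindles, so that broader claim goes beyond them. This is a cheap improvement to make before analysis, not a flaw that invalidates the aim.

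**What to change.** In 2.4.7.2, state that time windows marked as sleep on the simultaneous EEG are censored from the fcDOT series before the Pearson correlations are computed, as motion-censored frames are. Apply this primarily to Aim 2, and by the same rule wherever fcDOT connectivity is used. Report retained fcDOT minutes per session by delirium state. In the same edit, say whether the eyes-closed data enter the Aim 2 estimate. If the exclusion in 2.4.7.1 was always meant to cover fcDOT, the sentence simply records that.

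The rule rests on the plan's own premise that these motifs are not known in awake delirious patients, so on that premise it does not remove the delirious state itself.

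Costs:
- The EEG must be marked for sleep over the whole fcDOT recording. The plan describes online watching and a 1-minute analysis window, so a full-session sleep mask cannot be assumed to exist.
- Some fcDOT minutes are lost in sleepy sessions.
- Drowsiness without K-complexes or spindles remains, so the protection is partial.

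No new recordings or patients are needed.

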2.4.7.3 MRI Acquisition, Image Processing, and FC (Aim 3)

Structural and functional MRI will be performed at either the Center for Clinical Imaging and Research (CCIR), located on the 10th floor of Barnes Jewish Hospital, or the 5th floor Mallinckrodt Institute of Radiology (MIR). The two scanners are the same model and will be equipped with the identical MR sequences. The same MR sequence will be used for each scan. Preoperative testing: The patient will undergo an MRI scan at BJH within one month of surgery, either at the CCIR or in the MRI suite of 5th floor of MIR. A study physician will be present during the scanning of inpatients to improve safety and monitoring. A CAM assessment will be completed on the same day as the scan. Pulse oximetry may be used during data acquisition, with the administration of supplemental oxygen, if needed. Session 4: The patient will undergo an MRI scan during the period between disconnection of chest tubes and within 1 month after hospital discharge at BJH, either at the CCIR or in the MRI suite of the 5th floor of MIR. A study physician will attend inpatient scans to improve safety and monitoring. A CAM assessment will be completed on the same day as the scan. Pulse oximetry may be used during data acquisition, with the administration of supplemental oxygen, if needed.

Image acquisition, preprocessing, and FC analysis will be performed as recently described[41] with minor modifications. Participants will be instructed to remain still and awake with eyes open during scans. Data will be uploaded into CNDA, which is a database used exclusively by Washington University in St. Louis to manage, share, and analyze imaging data. This database will be used to store acquired images, perform various analyses, and share data amongst collaborators. Only de-identified data will be stored in the database. Preprocessing includes motion correction, resampling in Talairach atlas space (3 x 3 x 3 mm cubic voxels), and intensity normalization to a whole-brain mode value of 1000[63]. We will employ motion censoring using the DVARS measure [57, 64] set at 04% root-mean-square frame-to-frame BOLD signal change[65], a critical step in reducing FC changes related to motion artifact. Additional noise reduction will be done via regression of CSF, white matter, and whole brain global signal. For FC analysis 9 x 9 x 9 mm cubes with at least 50% gray matter will be used. ROIs will have been assigned to 1 of 7 RSNs[66] with over 95% probability. Pearson correlations will be Fisher z-transformed prior to averaging to maximize normality. The median DMN FC taken across all DMN region pairs will serve as our summary metric for DMN integrity at an individual level.

